6.2.3. Vital Signs

Single sitting blood pressure, pulse measurements and temperature will be taken at times detailed in the Schedule of Activities given in the protocol.

The last pre-dose measurement at Day 1 will be used as the baseline. The maximum increase from baseline will be calculated by first subtracting the baseline value from each post-dose measurement to give the change from baseline. The maximum of these values over the respective period will then be selected, except in the case where a subject does not show an increase. In such an instance, the minimum decrease should be taken.

Similarly, the maximum decrease from baseline will be determined by selecting the minimum value of the changes from baseline. In cases where a subject does not show a decrease, the minimum increase should be taken.

6.2.4. ECG

A single 12-lead ECG will be obtained on all participants at screening and follow-up. *ECGs will be collected in triplicate in Part A on Days 1 and 2, in Part B on Days 1, 2 and 29. The Day 1 ECG values will serve as each subject's baseline values*

The QT, QTc, PR, RR, QRS and heart rate will be recorded at each assessment time.

If not supplied, QTcF will be derived using Fridericia's heart rate correction formula:

$$QTcF = QT / (RR)^{1/3} \quad \text{where } RR = 60/\text{HR} \text{ (if not provided)}$$

If not supplied, QTcB will be derived using Bazett's heart rate correction formula:

$$QTcB = QT / (RR)^{1/2} \quad \text{where } RR = 60/\text{HR} \text{ (if not provided)}$$

The average of the triplicate readings collected at each assessment time will be calculated for each ECG parameter. Baseline will be defined as the average of the triplicate pre-dose recordings at Day 1.

The maximum absolute value (post-dose) and the maximum increase from baseline for QTcF, QT, heart rate, PR and QRS, will be determined over the first 12 hours postdose for Day 1 and Day 29 (part B only) separately, and also over all measurements taken postdose for QTcF, PR and QRS.

The maximum increase from baseline will be calculated by first subtracting the baseline value from each post-dose measurement to give the change from baseline. The maximum of these values over the respective period will then be selected, except in the case where a subject does not show an increase. In such an instance, the minimum decrease should be taken.

6.2.5. Other Safety Data

Additional safety data will be collected as described in the protocol and will be listed as necessary.

6.3. Pharmacokinetic Endpoints

Blood samples for PK analysis of PF-06835375 will be taken according to the Schedule of Activities given in the protocol.

The following PK parameters that will be calculated for PF-06835375 (if possible) for PF-06835375 for Part A (see Table 2) and Part B (see [Table 3](#)) from the concentration-time values using standard non-compartmental methods.

Table 2. Noncompartmental PK Parameters for Part A (Single Ascending Dose)

Parameter	Analysis Scale	PF-06835375
AUC ₆₇₂	ln	D
AUC _{last}	ln	D
CCI	[REDACTED]	[REDACTED]
AUC _{inf} *	ln	D
AUC _{inf(dn)} *	ln	D
C _{max}	ln	D
CCI	[REDACTED]	[REDACTED]
T _{max}	R	D
CCI	[REDACTED]	[REDACTED]
[REDACTED]	[REDACTED]	[REDACTED]
[REDACTED]	[REDACTED]	[REDACTED]
[REDACTED]	[REDACTED]	[REDACTED]

Key: A=analyzed using statistical model, D=displayed with descriptive statistics, ln=natural-log transformed, R=raw (untransformed), *=if data permits

Table 3. Noncompartmental PK Parameters for Part B (Multiple Ascending Dose)

Parameter	Dosing Day	Analysis scale	PF-06835375
AUC τ	1, 29	ln	D
CC1			
CC2			
CC3			
C _{av} (dn)	1, 29	ln	D
AUClast	1, 29	ln	D
AUClast (dn)	1, 29	ln	D
C _{max}	1, 29	ln	D
CC4			
CC5			
CC6			
CC7			
T _{max}	1, 29	R	D
CC8			
CC9			
CC10			
CC11			
C _{min}	29	ln	D
PTF	29	ln	D
R _{ac}	29	ln	D
R _{ac} C _{max}	29	ln	D
Key: A=analyzed using statistical model, D=displayed with descriptive statistics, ln=natural-log transformed, R=raw (untransformed), *=if data permits			

6.4. Pharmacodynamic (PD) Endpoints that Will be Addressed in SAP

Change from baseline will be explored for the concentrations of following biomarkers.

1. Circulating CXCR5 positive B cells, cTfh cells.

CC1

CC1

CCI

CCI

6.7. Covariates

None.

7. HANDLING OF MISSING VALUES

For the analysis of safety endpoints, the sponsor data standard rules for imputation will be applied.

7.1. Concentrations Below the Limit of Quantification

In all data presentations (except listings and PK analyses), concentrations below the limit of quantification (BLQ) will be set to LLOQ/2, where LLOQ denotes the lower limit of quantification. For the PK analyses the concentrations below the limit of quantification (BLQ) will be set to zero.

(In listings BLQ values will be reported as “<LLOQ”, where LLOQ will be replaced with the value for the lower limit of quantification).

7.2. Deviations, Missing Concentrations and Anomalous Values

In summary tables and plots of median profiles, statistics will be calculated having set concentrations to missing if 1 of the following cases is true:

1. A concentration has been collected as ND (ie, not done) or NS (ie, no sample).
2. A deviation in sampling time is of sufficient concern or a concentration has been flagged anomalous by the pharmacokineticist.

Note that summary statistics will not be presented at a particular time point if more than 50% of the data are missing.

7.3. Pharmacokinetic Parameters

Actual PK sampling times will be used in the derivation of PK parameters.

If a PK parameter cannot be derived from a subject's concentration data, the parameter will be coded as NC (ie, not calculated). (Note that NC values will not be generated beyond the day that a subject discontinues).

In summary tables, statistics will be calculated by setting NC values to missing; and statistics will be presented for a particular dose with ≥ 3 evaluable measurements.

If an individual subject has a known biased estimate of a PK parameter (due for example to deviation in dosing), this will be footnoted in summary tables and will not be included in the calculation of summary statistics or statistical analyses.

8. STATISTICAL METHODOLOGY AND STATISTICAL ANALYSES

8.1. Statistical Methods

As this is an exploratory study, no formal hypothesis testing will be performed.

8.2. Statistical Analyses

8.2.1. Analysis of Efficacy Data

Standard descriptive summaries will be presented for SLEDAI-2K (SLE patients) and DAS28 (RA patients).

8.2.2. Pharmacokinetic Analysis

To assess the pharmacokinetics of PF-06835375, the PK parameters detailed in [Section 6.3](#) will be listed and summarized for participants in the PK analysis set (as defined in [Section 5.2](#)). Missing values will be handled as detailed in [Section 7](#). Each PK parameter will be summarized by dose which will be performed separately for the SAD and MAD parts of the study. Each summary will include the set of of summary statistics as specified in the [Table 4](#) for SAD and [Table 5](#) for the MAD respectively.

Table 4. PK Parameters to be Summarized Descriptively for Part A (Single Ascending Dose)

Parameter	Summary Statistics
C_{max} , AUC_{last} , $AUC_{last}(dn)$, AUC_{672} , C_{max} , C_{min} , $C_{av}(dn)$, C_{max} , R_{ac} , C_{max}	N, arithmetic mean, median, cv%, standard deviation, minimum, maximum, geometric mean and geometric cv%.
T_{max}	N, median, minimum, maximum.
C_{max} , C_{min} , $C_{av}(dn)$, C_{max}	

Table 5. PK Parameters to be Summarized Descriptively for Part B (Multiple Ascending Dose)

Parameter	Summary Statistics
AUC_{t} , AUC_{last} , $AUC_{last}(dn)$, C_{max} , C_{min} , $C_{av}(dn)$, C_{max} , R_{ac} , C_{max}	N, arithmetic mean, median, cv%, standard deviation, minimum, maximum, geometric mean and geometric cv%.
T_{max}	N, median, minimum, maximum.
C_{max} , C_{min} , $C_{av}(dn)$, C_{max}	

There will be summary tables presenting all PK parameters. Visit will be included in the subheading of PK parameter summary table. PK parameters will be summarized descriptively by dose/treatment group in concordance with sponsor's reporting standard.

To assess the relationship between the PK parameters and dose, AUC_{last} (Part A only) and C_{max} will be plotted against dose (using a logarithmic scale), and will include individual subject values and the geometric means for each dose. Geometric means will have a different symbol than the individual values. The values will be dose normalized (to a 1 mg dose) by dividing the individual values and raw geometric means by dose. A footnote will be added to the plots to indicate that geometric means are presented and that data from both cohorts are presented on the plot.

Supporting data from the estimation of $t_{1/2}$ and AUC_{inf} will be listed by analyte where applicable: terminal phase rate constant (k_{el}); goodness of fit statistic from the log-linear regression (r^2); the percent of AUC_{inf} based on extrapolation ($AUC_{extrap}\%$); and the first, last, and number of time points used in the estimation of k_{el} . This data may be included in the clinical study report.

Some presentations for PF-06835375 concentrations will include:

- A listing of all concentrations sorted by subject ID, treatment group, dose, day and nominal time post dose. The concentration listing will also include the actual times. Deviations from the nominal time will be given in a separate listing.
- A summary of concentrations by treatment, dose, day and nominal time post dose, where the set of statistics will include n, mean, median, standard deviation, coefficient of variation (cv), minimum, maximum and the number of concentrations above the lower limit of quantification.
- Median concentrations time plots (on both linear and semi-log scales) against nominal time post first dose by treatment group and dose (all treatments on the same plot per scale, based on the summary of concentrations by treatment group, dose and time post dose).
- Mean concentrations time plots (on both linear and semi-log scales) against nominal time post first dose by treatment group and dose (all treatments on the same plot per scale, based on the summary of concentrations by treatment group, dose and time postdose).
- Individual concentration time plots by treatment group and dose (on both linear and semi-log scales) against actual time post dose (there will be separate spaghetti plots for each dose per scale).
- Individual concentration time plots by subject (on both linear and semi-log scales) against actual time post first dose [there will be separate plots for each subject].

The length of time used for the x-axes of these plots will be decided on review of the data, and will depend on how long the PF-06835375 concentration is quantifiable in the matrix.

For summary statistics, median and mean plots by sampling time, the nominal PK sampling time will be used, for individual subject plots by time, the actual PK sampling time will be used.

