Table 1. Predicted Median Human Exposures and Safety Multiples for Expected Doses					
Cohort	Proposed Human Dose	Predicted human exposure			Safety Multiples^c
		C_{max} ($\mu\text{g}/\text{mL}$)	AUC^a ($\mu\text{g}^*\text{day}/\text{mL}$)	C_{av} ($\mu\text{g}/\text{mL}$) ^b	C_{av}
Single-Dose Cohorts:					
A1	0.03 mg IV	0.0122	0.1210	0.00434	60100
A2	0.1 mg IV	0.0433	0.4220	0.0151	17300
A3	0.3 mg IV	0.1240	1.23	0.044	5930
A4	1 mg IV	0.42	4.18	0.149	1750
A5	3 mg IV	1.24	11.9	0.424	616
A6	10 mg IV	4.2	40.8	1.46	179
A7	30 mg IV	12.7	123	4.38	59.6
A8	100 mg IV	40.3	402	14.4	18.1
Repeat-Dose Cohorts:					
B1	0.3 mg SC ^d	0.0314	0.591	0.0211	12400
B2	1 mg SC ^d	0.107	1.96	0.0699	3730
B3	3 mg SC ^d	0.32	5.85	0.209	1250
B4	10 mg SC ^d	1.08	19.5	0.698	374
B5	30 mg SC ^d	3.3	59.3	2.12	123

a. Single dose: AUC_{inf} ; Multiple dose: AUC_{tau} after 2nd dose where $\tau = 28$ days.
 b. C_{av} is calculated as AUC divided by 28 days.
 c. Based on exposure stopping limit of $C_{av} = 261 \mu\text{g}/\text{mL}$, determined as 1/10th of the NOAEL mean C_{av} exposure of 2610 $\mu\text{g}/\text{mL}$.
 d. SC bioavailability assumed to be 60%.

AUC = Area under the curve; C_{av} = Average observed concentration; C_{max} = Maximum observed concentration; IV = Intravenous; NOAEL = No observed adverse effect level; SC = Subcutaneous.

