9.3.2. Derivation of Pharmacokinetic Parameters

PK parameters for PF-06835375 following single and multiple dose administration will be derived from the concentration-time profiles by non-compartmental analysis as described in [Table 5](#) and [Table 6](#). Additional PK analyses may be performed if deemed appropriate. The PK parameters will be calculated using actual time and summarized descriptively by dose and regimen in accordance with Pfizer data standards. Details of the analysis will be provided in the SAP.

Table 5. PF-06835375 Serum Pharmacokinetic Parameters for Single Ascending Dose (SAD) Phase

Parameter	Definition	Method of Determination
C_{\max}	Maximum serum concentration	Observed directly from data
T_{\max}	Time at which C_{\max} occurred	Observed directly from data as time of first occurrence
CCI		
AUC_{last}	Area under the concentration-time profile from time 0 to the time of the last quantifiable concentration (C_{last})	Linear/log trapezoidal method
AUC_{inf}^a	Area under the concentration-time profile from time 0 extrapolated to infinite time	$AUC_{\text{last}} + (C_{\text{last}}^*/k_{\text{el}})$, where C_{last}^* was the predicted serum concentration at the last quantifiable time point estimated from the log-linear regression analysis
CC		
$AUC_{\text{last}}(\text{dn})$		
$AUC_{\text{inf}}(\text{dn})^a$	Dose normalized AUC_{last} Dose normalized AUC_{inf}	$AUC_{\text{last}}/\text{dose}$ $AUC_{\text{inf}}/\text{dose}$
CI		

a. If data permitted.

Abbreviations: CCI [REDACTED]; dn = Dose normalized to 1 mg; DOF = Duration of the IV infusion dose; IV = Intravenous.

PK parameters following multiple dose administration will be derived from the concentration time profiles of the repeat dose cohorts as follows:

Table 6. PF-06835375 Serum Pharmacokinetic Parameters for Multiple Ascending Dose (MAD) Phase

Parameter	Definition	Method of Determination
$AUC_{\tau_{\text{au}}}$	Area under the concentration-time profile from time 0 to time τ_{au} , the dosing interval, where $\tau_{\text{au}} = 28$ days	Linear/log trapezoidal method
AUC_{last}	Area under the concentration-time profile from time 0 to T_{last}	Linear/log trapezoidal method
C_{max}	Maximum serum concentration during the dosing interval	Observed directly from data
T_{max}	Time at which C_{max} occurred	Observed directly from data as time of first occurrence

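### The only AUC plotted against dose in Part A is AUClast per mg, which can fall short at the lowest doses through assay truncation and make linear exposure look more than dose-proportional

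*SAP*

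**What the plan says.** SAP 8.2.2 names one output for the relation between PK parameters and dose. It covers Cmax and, in Part A, AUClast, both of which "will be plotted against dose (using a logarithmic scale), and will include individual subject values and the geometric means for each dose". On scaling it adds: "The values will be dose normalized (to a 1 mg dose) by dividing the individual values and raw geometric means by dose".

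Protocol 9.3.2 (Table 5) defines AUClast as the "Area under the concentration-time profile from time 0 to the time of the last quantifiable concentration", so its endpoint depends on the assay limit. SAP 7.1 adds: "For the PK analyses the concentrations below the limit of quantification (BLQ) will be set to zero". Neither document states the LLOQ of the PK assay. No common time window, truncation check or limit on extrapolation is attached to the plot.

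The plot is not the only place where exposure appears by dose. SAP 8.2.2 also says: "Each PK parameter will be summarized by dose which will be performed separately for the SAD and MAD parts of the study". The legible rows of SAP Table 2 include AUC672, AUCinf and AUCinf(dn) for Part A, the last two only if data permit. SAP Table 3 includes AUCtau and Cav(dn) for Part B. SAP 8.2.2 also lists AUCextrap%. Rows of these tables are redacted, and nothing is inferred from their absence.

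**The concern.** The doses used in Part A run from 0.03 to 6 mg (SAP 2.1, Table 1), a 200-fold range. A low-dose profile starts close to any realistic assay limit and is cut off early. A high-dose profile is followed almost to its end. Dividing each AUClast by dose does not correct for this, because the missing share of the area is larger at low doses. The plotted value per mg then climbs with dose although clearance is constant.

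The direction matters for this molecule. PF-06835375 binds and depletes CXCR5-positive cells, and exposure per mg that rises with dose is what target-mediated clearance would produce. A reader could not tell that from truncation on the AUClast plot alone.

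**Working it through.** **Inputs from the documents.** Predicted exposures are in Protocol Table 1 (Section 1.3). At 0.03 mg IV, Cmax is 0.0122 µg/mL (12.2 ng/mL) and AUCinf is 0.1210 µg·day/mL. Doses used are in SAP Table 1. Protocol 1.6 says that 16 weeks exceed five half-lives, so the terminal half-life is below 112/5 = 22.4 days.

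**Assumptions.** LLOQ of 0.1, 1, 5 or 10 ng/mL, and the shape of disposition, which Table 1 does not identify.

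**1. Reproduce Table 1.** Cav = AUC/28 and safety multiple = 261/Cav.
- A1: 0.1210/28 = 0.00432, multiple 60,397 (stated 0.00434 and 60,100).
- A8: 402/28 = 14.36, multiple 18.2 (stated 14.4 and 18.1).

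All eight single-dose rows agree within 3%.

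**2. Table 1 is linear.** AUCinf per mg lies between 3.97 and 4.22 from 0.03 to 100 mg (log-log slope 0.998). Cmax per mg lies between 0.403 and 0.433 (slope 0.999). The geometric means are 4.09 µg·day/mL and 0.416 µg/mL per mg. Any trend below therefore comes from truncation.

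**3. Hand check, one exponential.** With C(t) = C0·exp(−kt), AUClast = (C0 − LLOQ)/k and AUCinf = C0/k, so the captured share is 1 − LLOQ/C0.
- At 0.03 mg, C0 = 0.03 × 416.5 = 12.5 ng/mL. The share is 0.92 at LLOQ 1, 0.60 at LLOQ 5 and 0.20 at LLOQ 10.
- At 6 mg, C0 = 2,499 ng/mL. The share is 0.998 at LLOQ 5.
- False ratio of AUClast per mg, 6 mg to 0.03 mg, at LLOQ 5: 0.998/0.60 = 1.66.

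The implied half-life is 0.693 × 4.09/0.416 = 6.8 days. This is the mildest case examined.

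**4. Two exponentials.** The models are scaled to the same Cmax and AUC per mg, with assumed distribution half-lives of 1-4 days and terminal half-lives of 14-22.4 days. AUClast is taken to the last time at or above LLOQ, capped at 112 days after dosing. It is computed on the continuous profile and on the Part A visit days. The table gives the range over these models and the one-exponential case. The 0.1 ng/mL row uses the continuous profile.

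| LLOQ (ng/mL) | AUClast/AUCinf at 0.03 mg | At 6 mg | False 6 mg : 0.03 mg ratio per mg | Apparent log-log slope |
|---|---|---|---|---|
| 0.1 | about 97-99% | about 97-100% | about 1.0 | about 1.00 |
| 1 | 64-92% | 97-100% | 1.09-1.57 | 1.01-1.07 |
| 5 | 8-60% | 97-100% | 1.7-12 | 1.08-1.41 |
| 10 | 3-20% | 97-100% | about 5 to more than 20 | 1.24 to about 1.6 |

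A slope of 1 is proportional. At an LLOQ of 20 ng/mL or more, the predicted 0.03 mg profile is never quantifiable.

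**5. One full profile.** Two-compartment model with a 2-hour infusion. CL = 10/40.8 L/day and V1 = 10/4.2 L come from the 10 mg row. V2 = 2.5 L and Q = 0.7 L/day are assumed. Captured share at 0.03, 0.1, 0.3 and 6 mg:
- LLOQ 1: 0.76, 0.94, 0.99, 1.00
- LLOQ 5: 0.20, 0.53, 0.88, 1.00
- LLOQ 10: 0.04, 0.35, 0.76, 0.99

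**6. Does AUCinf repair it?** In the step 5 model, non-compartmental AUCinf recovers the true value from 0.3 mg upward. At 0.03 mg with LLOQ 5-10 it recovers only about 0.2 to 0.5 of it, because the terminal slope is fitted before the terminal phase. AUCextrap% then understates the loss. With 0.20 captured and, say, 0.38 recovered, it would read 1 − 0.20/0.38 = 47%, while 80% is missing.

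**7. Does AUC672 repair it?** Not if values below the limit are set to zero inside the window. In the step 5 model, AUC672 per mg at 0.03 mg relative to 6 mg is then 1.00, 0.38 and 0.09 at LLOQ 1, 5 and 10.

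**The case against.** A reader might infer more than the documents support.

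- **That dose proportionality is judged only from these plots.** It is not. Every SAP 6.3 parameter is summarised by dose, including AUCinf(dn) and AUC672 in Part A and AUCtau and Cav(dn) in Part B. The gap is that AUCinf(dn) is tabulated but not plotted. The tables are a weak safeguard at the lowest doses: SAP 7.3 needs at least three evaluable values, and A1-A4 plan three active subjects each. One non-calculable AUCinf removes that dose.
- **That exposure per mg is bound to appear to rise.** The LLOQ is not stated. At 0.1 ng/mL the loss at 0.03 mg is about 1-3%, and the plot would be sound. At 1 ng/mL the effect lies mostly in one cohort of three active subjects.
- **That the Cmax plot or Part B shares the problem.** Cmax is not truncated unless it is itself near or below the LLOQ, and the AUClast plot is for Part A only.
- **That a decision rests on the plot.** None does. SAP 4 and 8.1 exclude hypothesis tests and decision rules, Protocol 9.1 excludes formal inference for PK, and exposure stopping (Protocol 3.4.2) uses Cav against 261 µg/mL.

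A careful reader could also detect truncation from the individual semi-log profiles, the counts above LLOQ and the AUCextrap% listing. All of this stands, and it limits the point. It does not make AUClast per mg a comparable measure across a 200-fold dose range, and the figure designated for the exposure-dose question carries no warning.

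**Conclusion.** The point holds conditionally. The mechanism and its direction are certain. The size depends on an LLOQ that the documents do not give and on a disposition shape that Table 1 does not fix. The distortion ranges from negligible at 0.1 ng/mL to severalfold or more at 5-10 ng/mL, and it is concentrated at 0.03 and 0.1 mg. The figures rest on strictly linear kinetics scaled to Table 1's predicted medians, not on observed data. This is a weakness in a descriptive display. It is worth correcting because the remedy uses parameters that are already planned, but it is not a flaw in any formal conclusion.

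**What to change.** In SAP 8.2.2, for Part A, add one of the following:

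- a plot of AUCinf(dn) against dose, limited to subjects whose AUCextrap% is below a limit set in advance, with other doses marked as not estimable; or
- a plot of a dose-normalised partial AUC over a window in which concentrations are quantifiable at every compared dose.

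The extrapolation limit is essential. Without it, the AUCinf plot would carry its own downward bias at the lowest doses (step 6 of the working). Keep AUClast(dn) as a supporting plot, with a footnote stating the LLOQ and that low-dose values are truncated. No Part B change follows from this argument.

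The cost is one extra figure and a footnote. AUCinf(dn) and AUCextrap% are already produced; the partial AUC would need a window to be defined. The price is that the lowest doses may drop out of the AUCinf plot. Showing them as not estimable is more honest than plotting truncated values as comparable.

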8.2.3. Pharmacodynamic Analysis

All of the PD endpoints described in the [Section 6.4](#) will be summarized by dose at each time point presented in tabular form or graphically. The descriptive statistics will include standard summaries of absolute concentrations, changes from baseline and percentage change from baseline. The presentations of PD endpoints will include:

- Listing of B and TfH cells sorted by subject ID, treatment group, dose and visit.
- Summary of B and cTfh Cell Depletion Parameters (Mean maximum % decrease from baseline, Mean duration of depletion below 10 cells/ μ L after first dose) following Single Dose Intravenous Administration.

C
C
I
C
C
I
C
C
I
C
C
I

The length of time used for the x-axes of these plots will be decided on review of the data, and will depend on follow-up duration of participants.

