3.5. Criteria for End of Study

All subjects will be followed through the Week 16 visit. In order for the Week 16 visit to be the subject's last clinic study visit, B cell counts meet at least one of these criteria:

- B cell count is \geq 50% of baseline value AND is stable or increasing between Week 12 and Week 16 measurements, OR
- B cell count is \geq lower limits of normal (defined as 80 cells/ μ l¹⁹) at Week 16.

If at least one of the above criteria are not met at Week 16, subjects will continue in the study and will be followed until B cell count meets at least one of these criteria:

- B cell count is \geq 50% of baseline value AND is stable or increasing between the two measurements at least two weeks apart, OR
- B cell count is \geq lower limits of normal (defined as 80 cells/ μ l¹⁹), OR
- B cell count reaches a new stable (or increasing) detectable level AND subject is clinically stable for minimum of two consecutive visits, each at least two weeks apart, based on the assessment by both the sponsor AND the investigator. The earliest B cell count that can be considered for this criterion is from the Week 20 visit. As a result, subjects will not be discharged prior to availability of Week 24 lab results for B cells under this criterion.

B-cell counts obtained from CLIA certified central lab will be used for this determination.

Baseline value is defined as the average of Screening and Day 1 pre-dose values. In cases where only one value (ie, screening or Day 1 pre-dose) is available, this one value will be used as the baseline. Stable is defined as ± 5 cell/ μ l. Values obtained by the central lab will be used.

B cell counts data will be available only after subject completes the clinic visit due to the required shipment of samples to central lab and their processing time. Once subject meets the criteria for the end of study described above, a phone visit will take place within approximately 1-2 weeks, prior to the next scheduled in clinic visit. This phone visit will be considered the end of study visit/last visit.

Subjects may be asked to return for additional follow up visits beyond the anticipated end of study visit for safety reasons as determined by the Investigator in consultation with the sponsor medical monitor.

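### By-visit B-cell means after Week 16 leave out subjects already discharged on their B-cell count, so they tend to understate recovery

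*SAP*

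**What the plan says.** - **Summaries.** SAP 8.2.3 states that the PD endpoints of SAP 6.4, which include circulating CXCR5-positive B cells and cTfh cells, "will be summarized by dose at each time point presented in tabular form or graphically". The statistics are absolute values, changes and percentage changes from baseline. The time axis of the plots "will depend on follow-up duration of participants".
- **Follow-up.** Protocol 3.5: "All subjects will be followed through the Week 16 visit". Week 16 is a subject's "last clinic study visit, B cell counts meet at least one of these criteria": at least 50% of baseline and stable or rising since Week 12, or at least 80 cells/µL. Otherwise "subjects will continue in the study and will be followed until B cell count meets at least one of these criteria". The later list repeats those two and adds a third: a new stable or rising detectable level in a clinically stable subject over two visits, which cannot lead to discharge before the Week 24 results.
- **Missing data.** SAP 7.2: "Note that summary statistics will not be presented at a particular time point if more than 50% of the data are missing".
- **Endpoint timing.** In Protocol Section 2 the secondary cell-depletion endpoint is set at Day 29 for single doses and Week 8 for multiple doses.

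**The concern.** After Week 16, whether a subject still has a B-cell value depends on the B-cell value itself. A mean over those still attending then estimates something other than the cohort's mean count, and in general a lower figure. SAP Section 2 names the magnitude and duration of both depletion and recovery as a PD aim. The readable depletion parameters in SAP 8.2.3 (maximum percentage decrease and duration below 10 cells/µL, after single IV doses) do not measure return to 50% of baseline or to 80 cells/µL. A reader would therefore look to the by-visit summaries for recovery, and depletion could appear longer and deeper than it was. Late placebo comparators would also be few: Protocol 4.2 excludes screening counts below 80 cells/µL, so most placebo subjects should meet an exit criterion at Week 16.

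**Working it through.** **No figure to reproduce.** The documents give no recovery times, no spread and no share discharged per visit.

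**Closed form.** Let p be the share still followed at a visit, and k the mean count of discharged subjects (had they been measured) divided by the mean count of those remaining. Then

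true mean / displayed mean = p + (1 − p)k.

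Through Week 16, p = 1 as far as planned discharge goes, so the ratio is 1.00. Later it exceeds 1 whenever k > 1. A ratio of 2 needs k = (2 − p)/(1 − p):

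- p = 0.75: 1.25/0.25 = 5.0
- p = 0.50: 1.50/0.50 = 3.0
- p = 0.25: 1.75/0.75 = 2.33

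**Simulation of the Protocol 3.5 exits. All inputs are assumptions:** lognormal baseline cut off at 80 cells/µL, median about 180; a Hill recovery curve; log-SD of visit noise 0.2 in the examples below; first two exit criteria only. Each cell gives the share present, then the true/displayed ratio for counts.

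| Median time to 50% recovery | Log-SD of that time | Week 20 | Week 24 | Week 28 |
|---|---|---|---|---|
| 24 weeks | 0.2 | 84%, 1.22 | 57%, 1.45 | 31%, 1.66 |
| 24 weeks | 0.4 | 74%, 1.52 | 54%, 1.77 | 38%, 2.00 |
| 24 weeks | 0.8 | 64%, 2.27 | 53%, 2.61 | 43%, 2.87 |
| 36 weeks | 0.2 | 99%, 1.03 | 94%, 1.11 | 83%, 1.25 |

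The closed form ties these together. In the second row at Week 24, k = (1.77 − 0.54)/0.46 = 2.67.

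**Wider grid.** Median recovery 12 to 48 weeks, log-SD 0.2 to 0.8, noise 0.1 to 0.3, three curve steepnesses, and the third criterion used by 0, 50 or 100% of subjects. At visits from Week 20 with at least half present:

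- counts: median ratio 1.5, 5th to 95th percentile 1.0 to 2.9
- percent of baseline: median 1.3, 5th to 95th percentile 1.0 to 2.6

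**A second model** (logistic recovery, log-SD 0.4, 15% visit noise) at Week 24: with half-recovery at Week 24, the true mean is 41% of baseline against 25% displayed (41/25 = 1.6). With half-recovery at Week 32, it is 24% against 16% (24/16 = 1.5).

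**What SAP 7.2 would do.** If it covers PD and counts discharged subjects as missing, a cohort with 6 active subjects loses its summary once 4 have left (4/6 = 67%). With 3 gone (50%), a three-subject mean is still shown. A cohort with 3 active loses it once 2 have left.

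**The case against.** **SAP 7.2 is a cut-off.** A reader might infer that late PD means are displayed without limit. The documents do not support that. The rule stands in the SAP's missing-values section and governs concentrations: "In summary tables and plots of median profiles, statistics will be calculated having set concentrations to missing". SAP 6.4 uses the same word for PD: "Change from baseline will be explored for the concentrations of following biomarkers". But 7.2 also refers to the pharmacokineticist, and it does not say whether a discharged subject counts as missing. Even if applied in full, it leaves the ratios above at visits with half or more present.

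**The third criterion changes the picture.** It lets subjects leave below both recovery thresholds. In the simulation with 24-week median recovery, only 1 to 3% remain at Week 28 if everyone uses it, so under 7.2 the last visit shown would be Week 24. This stands as a limit on how far the bias runs. It does not alter Weeks 20 and 24, which precede any exit by that route.

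**Late means do not describe only non-recoverers.** A subject contributes the visit at which a criterion is met. In the logistic model, 26% of Week 24 contributors were at a recovery threshold when half-recovery was at Week 24.

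**cTfh.** Discharge uses B-cell counts, so cTfh values are not selected on themselves. Any distortion runs through their correlation with B cells.

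**Redaction.** Several display items in SAP 8.2.3 are blacked out, and the SAP's amendment section mentions a separate bSAP. Individual profiles or a recovery display cannot be called absent.

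**Descriptive study.** No hypothesis is tested, and the Day 29 and Week 8 endpoints precede any planned discharge. Both points are right and confine the matter to the description of recovery.

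**Conclusion.** The point holds for by-visit B-cell summaries from Week 20 on. They exclude subjects discharged at earlier visits because of the summarised variable, and the readable text of SAP 8.2.3 sets no last visit and no handling for them. The direction is toward understating recovery. A two-fold understatement is tempting to quote, but it is one value in a range of about 1.0 to nearly 3 for counts at visits with at least half present. It depends on the assumed spread of recovery times, and tightly clustered recovery brings the ratio close to 1. SAP 7.2, if it applies, limits the effect without removing it.

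The Day 29 and Week 8 endpoints are unaffected, and cTfh is affected only indirectly. Duration below 10 cells/µL is largely unaffected: the two recovery criteria sit at 80 cells/µL and at about 40 or more (50% of a baseline near or above 80), so only a third-criterion exit could cut that duration short.

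**What to change.** In SAP 8.2.3:

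1. Restrict by-visit mean, change and percentage-change summaries, and any mean plots, of B cells (and cTfh) to visits through Week 16.
2. After Week 16, show individual profiles with n per visit.
3. Describe recovery by time from Day 1 to a B-cell count of at least 50% of baseline or at least 80 cells/µL. Show subjects who leave under the third criterion as a separate outcome, for example a competing event in a cumulative incidence display. Plain Kaplan-Meier censoring would be informative, because these subjects leave below the threshold with recovery settled or slow.

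Carrying forward the last value of discharged subjects is not a good substitute, since it freezes each subject at the discharge value.

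The cost is SAP wording and one extra display, with no change to study conduct. The downside is that mean curves stop at Week 16.
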